1. SPIED Study Emergency Department Data Form [Appendix 4]
 - a. Emergency Department staff may choose to use this form in place of Medical Surveys should they prefer, or if there are logistical challenges encountered with Medical Surveys
2. Limb Observation Chart: [Appendix 6]
 - a. It is standard practice on the surgical ward for nursing staff to complete limb observations every 1-2 hours on patients with #NOF and record these on a limb observation chart.
 - b. This chart has been modified for the SPIED study to also record pain scores
 - c. Also includes pain score calculators for the VAS and PAINAD
3. Subjective Observed Patient Comfort During Nursing Cares [Appendix 7]

Primary outcome = reduction of pain score

VAS pain scores will be recorded at rest and on movement. Movement is defined as attempted hip flexion to 15 degrees. PAINAD scores will be single measure based on nursing observation.

This score will be documented at the following times:

- Prior to placement of nerve block in the emergency department
- 15, 30, 60 minutes post placement of block
- With routine limb observations on the surgical inpatient ward, approximately hourly

Data will be collected for 12 hours post nerve block (or the next documented score after 12 hours) or until the patient is moved to the operating room, whichever is sooner.

Sample size and statistical power

The rationale for sample size calculations:

- A reduction in visual analogue pain score of 13 mm (1.3/10) was established as being clinically significant by Todd et al in 1996 [26].
- A clinically significant difference between two treatments that reduce pain scores by 1.3/10 has not been well defined
- Cooper et al used 1.5/10 difference in pain scores as a definition of clinically significant difference between blocks [27].
- Newman et al found a standard deviation in pain score reduction of 2.4 in patients receiving regional analgesia for #NOF in 2013 [28]. This figure was used by Cooper et al for their power calculation in 2018.
- Cooper et al found standard deviations of 2.2 and 2.4 respectively for the FNB and FICB [27].
- A retrospective study of patients that received regional anaesthesia for # NOF at LBH in the first 4 months of 2019 was performed by co-investigators of this study. This data included 40 patients that received regional anaesthesia in ED, 6 of whom received a PENG block. Pain score documentation was not sufficiently reliable to inform power calculations for this observational study.

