Minimum Sample Size Calculation: Application of Student's t-Test.

Calculation assisted by using the Simple Sample Size Calculator (Android application). [Appendix 2]

- One-sided test to assess for non-inferiority
- Two sample
- Error 0.05
- Sample allocation ratio of 1:2
- Standard Deviation = 2.4
- $\mu_0 = 4$, $\mu_1 = 2.5$ (difference in pain score reduction of 1.5)
- Target (Actual) Power = 0.8000
- **Sample size = 74 (25+49)**

Duration of Data Collection

At our institution, we had 203 patients present with fractured neck of femur in 2018 and in the first 6 months of 2019 we have had 79. This is an average of 15.67 per month. Presuming this average continues and we achieve an enrolment rate of 80% and a PENG block delivered to one-third of these patients, we could expect to enrol sufficient patients in 6 months. To ensure significant power is achieved, we plan to enrol patients for a minimum of 6 and a maximum of 8 months.

Enrolment may be terminated early if we achieve a minimum enrolment of 125 patients and 41 PENG blocks. These numbers would allow for assessment of superiority (two-sided test) sensitive to a difference in pain score reduction of 1.3/10. [Appendix 3]

Secondary Outcomes

In an attempt to measure patient important outcomes, we will collect data on:

- Onset Time for analgesia (defined as the time until the first pain recorded pain score that is $\geq 1.5 / 10$ less than the pre-block pain score.
- Subjective observed patient comfort during nursing cares
- Patient preference where crossover occurs.
- Rates of block failure
- Block duration of analgesia

Subjective observed patient comfort during nursing cares:

Nursing staff caring for patients will be asked to comment on the patient's pain during standard nursing cares that require movement. These may include:

- Transfer to or from a bed
- Transfer on and off a bedpan
- Change of bedding or pad
- Other

At the time of nursing care, nurses are asked to rate the patient's analgesia as adequate or inadequate

Patient Preference where crossover occurs

- Some patients will have a repeat nerve block in the preoperative phase
- Of this population, some will receive a nerve block that is different to the block they received in ED. Hence they will have received cross over treatment and can act as their own control to compare two blocks.
- Investigators will identify these patients and they will be asked which block they found to provide more comfort.

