- Treatment in this phase of the patient's journey will be decided by the acute pain service or duty anaesthetist. The investigators will have no influence over which repeat block the patient receives.

Block failure

- Defined as maximum pain score improvement of less than 1.5 out of 10.

Duration of analgesia from nerve block

- End of block effect defined as an increase in pain score to ≤ 1.0 from pre-block pain score in a patient who had a reduction in pain score of > 1.5 at any time.

Opioid Requirement

- Opioid intake will be measured by analysis of the electronic medication chart from the insertion of block until 12 hours have passed, or the patient is checked in to the operating theatre, whichever occurs first.
- This information will be converted to milligrams of oral morphine using the Faculty of Pain Medicine Opioid Calculator

Adverse events

In an effort to detect the incidence of adverse events, the investigators will:

- Perform a keyword search of the “Continuous Doc” feature of the electronic record, after the patient is discharged from the hospital.
 - Keywords:
 - Delirium
 - Sedation
 - Constipation / Constipated
 - Aspiration
 - Naloxone
- Review the electronic medication chart for use of:
 - Naloxone
 - Antibiotics

Surgery Waiting Time:

Time to surgery will be defined as the time from Triage in the Emergency Department to the time of Check In at Operating Theatre for operative fixation.

Data collection on our cohort for the purposes of the primary outcome will cease at the time of check in to the operating theatre or at 12 hours after the insertion of nerve block, whichever is sooner.

Mean, median and longest wait times will be recorded. This information will inform future practice at our hospital.

Data Collection and Storage

Primary Data Recording Methods:

Were discussed above and are summarised here:

- ❑ Documentation in the electronic medical record record (PowerChart / FirstNet / SurgiNet) as is usual practice for all patients treated in the emergency department and those admitted to the hospital
- ❑ Documentation on the paper SPIED Limb Observation Chart [Appendix 6] which is usual practice for patients admitted to the inpatient orthopaedic and surgical ward with fractured neck of femur. The standard chart has been modified for the SPIED study to include pain scores and pain score calculators.

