- ❑ Documentation on a paper form SPIED ED Data Form [Appendix 4] in the emergency department. This is additional to usual documentation and may be replaced by utilising Medical Surveys for data entry in the ED.
- ❑ Subjective Observed Patient Comfort During Nursing Score. May be completed in paper form [Appendix 7] or within Medical Surveys.

Data Governance

Data Storage:

The completed SPIED ED Data Form [Appendix 4] will be filed by clinicians in a folder within the Acute clinical area of the Emergency Department at Lismore Base Hospital. The SPIED ED Data Form will be the enrolment record.. Completed forms will be frequently collected by the investigators and stored securely with the ED Support Offices, which require swipe card access. This data will be stored for 5 years after the completion of data collection and then destroyed.

All other paper forms associated with the SPIED Study will form part of the patient's hospital record and will be treated accordingly.

Data Access:

- Investigators who are clinicians at Lismore Base Hospital have access to the patient's electronic medical records in the usual fashion as they would for day to day clinical work.
 - Investigators who access a patient's file for the purpose of data collection rather than clinical care, will create an electronic entry to document that they are accessing the file for the purposes of the SPIED study.
- In the event that any research funding is obtained, a research assistant may have access to Medical Surveys data and eMR as do the investigators.

Statistical Analysis

Primary Outcome:

Reduction in pain scores over the first 12 hours after nerve block. We will apply the following statistical tests:

- Student's t-test to compare the reduction in pain score of patients who receive a PENGGB compared to FNB and FICB
 - Subgroup analyses of the cognitively impaired and non-cognitively impaired population. These populations will have pain scored by the PAINAD and VAS respectively.
 - Subgroup analysis of FNB and FICB separately

Secondary Outcomes

- Onset of block. Defined as the time until the first pain score ≥ 1.5 less than the pre-block pain score.
 - T-test
- Subjective observed patient comfort during nursing cares
 - Chi Square test
- Patient Preference in the event of crossover
 - Chi Square test
- Rates of block failure. Defined as not achieving a reduction in pain score of $\geq 1.5 / 10$
 - Chi square test

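### Block failure has no minimum pre-block score and no stop at a repeat block, so the recorded failure rate can be biased upward or downward

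*Protocol*

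**What the plan says.** The Block failure entry under Secondary Outcomes reads "Defined as maximum pain score improvement of less than 1.5 out of 10". The Statistical Analysis section restates it ("Rates of block failure. Defined as not achieving a reduction in pain score of" 1.5 or more) and assigns a chi-square test. The two wordings agree. Neither gives a time window, a minimum pre-block score, a choice between the rest and movement scores, or a rule for patients who receive a second block.

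Scores are taken before the block, then at "15, 30, 60 minutes post placement of block", and afterwards "With routine limb observations on the surgical inpatient ward, approximately hourly". The only stated limit on collection is in the primary outcome section: "Data will be collected for 12 hours post nerve block (or the next documented score after 12 hours"), or theatre if that comes sooner. The primary analysis covers the same period: "Reduction in pain scores over the first 12 hours after nerve block".

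The section on patient preference where crossover occurs says "Some patients will have a repeat nerve block in the preoperative phase", and that some of these will be of a different type from the emergency department block. The decision rests with the acute pain service or duty anaesthetist. Frequency and timing are not stated, and no section ends score collection at the repeat block.

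The Inclusion and Exclusion Criteria set no minimum pain score. Opioid given in the emergency department before the block is recorded, so some pre-block scores may already be lowered.

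**The concern.** Failure is meant to describe the first block. As written it also depends on two other things: how much pain the patient had beforehand, and whether anyone placed a second block.

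If pre-block pain is too low for a 1.5 improvement to be possible, the patient adds a failure that says nothing about the block. If a failed block is replaced while scoring continues, relief from the second block can satisfy the criterion and be credited to the first.

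The treating clinician chooses the first block, so low pre-block scores and repeat blocks may differ between the PENG group and the comparators. A difference in failure rates could then reflect patient selection or later care, and a true difference could be hidden. Scores after a second block also enter the duration outcome, which asks for a reduction at any time, and the primary reduction over 12 hours.

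**Working it through.** **The plan's own figures.** The protocol states no expected failure rate and no sample size for failure, so there is nothing to reproduce for this outcome. The minimum sample size for the primary outcome, 74 (25+49), is not affected. With a one-sided 0.05 error, 80% power, SD 2.4, difference 1.5 and ratio 1:2, the normal formula gives 1.5 × (2.4 × (1.645 + 0.842) / 1.5)² = 23.7. That rounds to 24 + 48 = 72. Power by the noncentral t at 25 and 49 is 0.809.

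**Step 1: low pre-block score.** Scores run from 0 to 10, so the largest possible improvement equals the pre-block score. The VAS is read in 1 mm steps, so anyone at 1.4 or below cannot improve by 1.5. This follows from the definition and needs no assumption.

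Let p be the true failure rate among patients able to show the improvement, and f the share starting below 1.5. The recorded rate is f + (1 − f)p. With p = 20% (assumed):

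| f (assumed) | Recorded rate |
|---|---|
| 5% | 0.05 + 0.95 × 0.20 = 24% |
| 10% | 0.10 + 0.90 × 0.20 = 28% |
| 20% | 0.20 + 0.80 × 0.20 = 36% |

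**Step 2: repeat block.** Let r be the share of failed first blocks repeated within the scoring window, and s the share of those that then improve by at least 1.5. The recorded rate is p(1 − rs). With p = 20% and s = 80% (both assumed):

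| r (assumed) | Recorded rate |
|---|---|
| 10% | 0.20 × (1 − 0.08) = 18.4% |
| 25% | 0.20 × (1 − 0.20) = 16% |
| 50% | 0.20 × (1 − 0.40) = 12% |

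**Step 3: both together.** The recorded rate is f + (1 − f)p(1 − rs). With f = 10% and r = 50% it is 0.10 + 0.90 × 0.12 = 20.8%, almost the assumed true 20%. With f = 20% and r = 25% it is 0.20 + 0.80 × 0.16 = 32.8%. With f = 5% and r = 50% it is 0.05 + 0.95 × 0.12 = 16.4%. The sign of the net error depends on quantities that the protocol does not give.

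**Step 4: the comparison.** Suppose both groups have a true rate of 20%, but 5% of one and 15% of the other start below 1.5. The recorded rates are 24% and 0.15 + 0.85 × 0.20 = 32%, a difference of 8 points with no difference between blocks. If instead r and s are equal in both groups, a true difference shrinks by the factor 1 − rs, which is 0.6 at r = 50% and s = 80%. At the minimum size, one patient classed differently moves the PENG rate by 1/25 = 4 points.

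**The case against.** The strongest reply is that the repeat-block part is inferred. The failure definition does not say that scores after a second block count. A repeat after 12 hours has no effect, and one inside the window matters only if the patient then improves by 1.5. How to handle later treatment is also something that an analysis plan often settles, and that plan is not shown. This stands as a limit on size and certainty. It does not remove the point: the protocol fixes an unrestricted maximum over a stated window and foresees repeat blocks before surgery. The low-score part needs no inference at all.

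Four stronger readings are tempting and are not supported:

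- A reader might infer that patients below 1.5 are all wrongly classified. They are always classed as failures, but some of their blocks may truly have failed. Their status cannot be measured on this criterion.
- A reader might infer that the best of many scores would turn a large, calculable share of useless blocks into successes through noise alone. That share depends on the noise SD and on the correlation between scores, and the documents give neither. The number of scores is also uncertain: ward observations are described as both about hourly and every 1–2 hours, and theatre may end them sooner.
- A reader might infer a push toward non-inferiority. Non-inferiority is the sample-size basis for the primary outcome, whereas failure is compared by a chi-square test. Step 3 leaves the net sign open, and step 4 shows that a spurious difference is also possible.
- A reader might conclude that failure should be judged at 60 minutes only. The Comparison of Nerve Blocks lists slow onset as a disadvantage of the FICB, so a single early cut-off could count late successes of that block as failures.

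**Conclusion.** The concern holds as a defect in a definition that the protocol fixes, and it is more than a missing detail: applying the rule as written gives a failure rate that does not describe the first block alone. The upward error is certain for every patient with a pre-block score below 1.5. The downward error can occur for every failed first block that is repeated within 12 hours. The percentages above are illustrations under assumed inputs. The actual size and net direction cannot be derived from the protocol. This affects a secondary outcome, and through the same scores the duration outcome and, to an unknown extent, the primary reduction. The sample size stands.

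**What to change.** **Failure.** Name the score (rest or movement), as the Statistical Analysis section does for duration by naming movement. Calculate the rate only among patients with a pre-block score of at least 1.5 on that score, and report the number below 1.5 in each group. Use only scores before any repeat block, and count a patient re-blocked before reaching a 1.5 improvement as a failure.

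**Duration.** Do not use scores after a repeat block. If these patients are censored at that time, replace the planned t-test with a time-to-event method, because a t-test cannot handle censored times.

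**Primary reduction.** Add a sensitivity analysis without scores after a repeat block. It should stay a sensitivity analysis: if failed blocks are repeated more often, cutting scores at that point is itself informative.

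**Cost.** The failure denominator becomes slightly smaller, the time of each repeat block has to be extracted, and there is a little more analysis work. A patient starting at exactly 1.5 must still reach zero to succeed, so the restriction makes success possible but not equally easy for everyone. Patient care and the sample size do not change.

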Short et al describes a quantifiable anatomical explanation for incomplete or failed anaesthesia from FNB or FICB in patients with #NOF. Several studies demonstrate that the FN block and FICB do not reliably block the obturator nerve or the lumbar plexus [16-22]. Distally, the high articular branches of the FN and AON are consistently located between the anterior inferior iliac spine and the iliopubic eminence [15]. The articular branches of the ON are located close to the inferomedial acetabulum. [15,23]. Subsequently the pericapsular nerve group block (PENGB) was designed to target the articular branches of the FN and AON by infiltrating the sub-psoas space at the level of the iliopubic eminence [23]. A case series of 5 consecutive patients with #NOF at Toronto Western Hospital was published in November 2018 and demonstrated the feasibility and efficacy of this block [23]. There is no published data describing the duration of analgesia provided by the PENG block.

The PENGB has subsequently been adopted by several practitioners at Lismore Base Hospital for the treatment of #NOF. We believe there is a study ongoing in peri-operative patients comparing PENGB to FICB in Toronto. We are not aware of any research into the utilisation of the PENGB in the emergency department setting. Searches of multiple study registries reveal no ongoing trials.

A retrospective study of patients that received regional anaesthesia for # NOF at LBH in the first 4 months of 2019 was performed. This data included 40 patients that received regional anaesthesia in ED, 6 of whom received a PENG block.

In this audit, patients' total opioid requirements from time of block to time of operation were recorded and converted to oral morphine equivalents using the ANZCA Faculty of Pain Opioid Calculator.

This audit found that patients receiving PENG blocks required fewer opioids pre operatively (mean = 22.67 mg) than did patients who did not receive a PENG block (FIB mean = 26.15 mg and FNB mean = 30.90 mg). Of note, patients receiving PENG blocks required fewer opioids in the 0-6 hours period immediately post block (mean = 3.00 mg) than did patients who did not receive a PENG block (FIB mean = 6.38 mg and FNB mean = 9.10). These results were not statistically significant ($p = 0.5$). The null hypothesis was retained. One adverse event relating to PENG blocks was documented in the records (failed block).

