All patients presenting to Lismore Base Hospital with fractured neck of femur (#NOF) are placed on the NOF pathway. The pathway suggests that patients on the NOF pathway should receive regional anaesthesia (nerve block) within 30 minutes of arriving at the Emergency Department. The nerve block performed will be determined by the treating clinician.

Inclusion and Exclusion Criteria

Inclusion Criteria

1. Adult patients (>18 years) presenting to Lismore Base Hospital Emergency Department with radiologically confirmed #NOF. The neck of femur fractures include:
 - a. Sub-capital fracture
 - b. Surgical neck fracture
 - c. Intertrochanteric fracture
 - d. Peritrochanteric fracture
2. The patient receives a nerve block for their fractured neck of femur in the Lismore Base Hospital Emergency Department
3. The nerve block may occur before or after the radiological confirmation of diagnosis

Exclusion Criteria:

1. Regional anaesthesia not provided in the Lismore Base Hospital Emergency Department
2. Allergy to amide local anaesthetics
3. Infection of the skin overlying at the overlying the site of potential nerve block
4. The patient has already received a nerve block for this fracture prior to arrival in at Lismore Base Hospital
5. Other reason at the discretion of clinician/s
6. Femoral shaft fracture

Block Standardisation

As this is an observational study, intervention is not dictated by the study, but is at the discretion of the treating physician. However, there have been efforts to standardise aspects of the care provided to improve the validity of this observational data.

In accordance with usual standards of practice:

- All nerve blocks are to be performed with ultrasound guidance. Needle tip and infiltration should be directly visualised with ultrasound.
- All nerve blocks are to be performed with continuous cardiac monitoring and intravenous access.

Nerve Block Kit:

To encourage standardisation of nerve blocks within hour department a nerve block kit is already in use. It contains:

- 80 mm x 21 gauge Pajunk SonoSpot needle (or alternative needle stocked by the department)
- 0.9% sodium chloride - 1 x 10mL vial
- 20 mL luer lock syringe
- 3 mL luer lock syringe
- Drawing up needle
- 25 gauge 38 mm or 23 gauge 35mm needle for local infiltration
- Dressing kit
- Chlorhexidine 2% in 70% ethanol skin prep solution (30 mL)
- Sterile ultrasound probe cover and gel

Standard Order Set:

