A standard order set [Appendix 1] has been built into FirstNet (the electronic medical record). This order set includes blood tests, radiography, referrals and analgesia. This “NOF order set” has been approved by the #NOF pathway working group and is available to all medical officers in the Emergency Department. The investigators will facilitate Medical Officers to add this order set to their ‘favourite’ orders.

Data To Be Collected

Regional Anaesthesia Provided

- Type of nerve block
- Content of nerve block
- Experience of practitioner

Patient Demographics

- # NOF Subtype
- Baseline characteristics: age, gender, comorbidities, social history, opioid use

Pain Scores

1. Visual Analogue Scale (VAS) [Appendix 6]
 - a. 100mm scale. Measured in 1mm increments. Converted to a score from zero to ten.
 - c. Measured at rest and on movement
2. Pain Assessment in Advanced Dementia (PAINAD) [Appendix 6]
 - a. Paper or electronic calculator
 - b. Scored zero to ten

Patients who are cognitively intact will have pain scores measured using the VAS, converted to score from zero to ten.

Patients who have a history of significant dementia or who clinically have significant cognitive impairment will have pain scored by a nurse or doctor using the pain assessment in advanced dementia (PAINAD) score, also zero to ten.

Subjective Observed Patient Comfort During Nursing Cares

- A binary measure of analgesia. Adequate or inadequate?

Opioid intake

- At baseline
- Pre-hospital
- In ED prior to regional analgesia
- After regional analgesia

Standard Documentation

Documentation that is recorded as a usual part of patient care

Nerve Block: Clinicians will be encouraged to document the placement of nerve block and its content in a standardised fashion within the patient's medical record, as is usual practice.

Pain Scores: Pain scores are recorded in the electronic medical record alongside vital signs. This is usual practice of nursing staff in the emergency department and on surgical wards. The utilisation of the VAS pain score is however, a departure from usual practice. Other pain scores such as the numerical pain scale and faces pain scale are previously / currently used by nursing staff at Lismore Base Hospital.

Analgesia Intake: Will be recorded in the electronic medical record. This is usual practice.

Additional Documentation

Documentation that is additional to usual practice, for the purpose of this study

Additional Paper Documentation:

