This project aims to improve understanding of the PENG block and its effects. We aim to publish results, either positive or negative, in a peer-reviewed journal approved by the Australasiaon College of Emergency Medicine and/or at appropriate scientific meetings.

Justice

All patients presenting to our facility with #NOF will be eligible for inclusion in this study. The patient experience of receiving the PENG block is very similar to that of receiving FNB or FICB and a lay-person would unlikely be able to tell the difference. There is no increased burden on patients enrolled nor on those not enrolled.

Beneficence

We believe that all patients present and future will benefit from the standardisation of practice and the establishment of preferred practice within our health service.

Risk

We do not anticipate that this study exposes participants to an increased risk. As outlined above we believe the PENG block conveys safety advantages compared to standard blocks the FNB and FICB. Most important is the physical separation of the site and the tissue plane of infiltration from major blood vessels. This reduces the risk of local anaesthetic systemic toxicity - which is the most serious adverse event associated with regional anaesthesia. Additionally, the nerves targeted and affected by the PENGGB are small, sensory nerves. Any trauma or toxicity to nerves as a result of a PENGGB would have no effect on motor nerves, which provide power to the thigh. Conversely, both the FICB and FNB effect larger motor nerves and any nerve trauma or toxicity can theoretically affect the muscle power in the thigh. We note that there is poor evidence supporting the argument that regional anaesthesia causes clinically significant trauma or toxicity to motor nerves.

Outcomes and Significance

The PENG block is a new therapy with a sound scientific basis and promising preliminary results both in the limited existing literature and our experience delivering this therapy at Lismore Base Hospital. If it is a superior regional analgesic then it follows that the therapy should be superiorly opioid-sparing. As we know, the study population is particularly at risk of complications from opioid analgesia [5-7]. Also, we know that pain (a result of ineffective analgesia) itself is a risk factor for agitation and delirium [reference] [29-33]. It follows that there would be an improvement in patient safety and patient-important outcomes from wider adoption of a superior intervention.

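### Opioid requirement is defined as all opioid charted after the block, so any continuing regular opioid is counted together with opioid needed because of the block's performance

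*Protocol*

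**What the plan says.** - **Definition** (Protocol, Opioid Requirement): "Opioid intake will be measured by analysis of the electronic medication chart from the insertion of block until 12 hours have passed", or until theatre check-in if that comes first. On units: "This information will be converted to milligrams of oral morphine using the Faculty of Pain Medicine Opioid Calculator". Regular and newly prescribed opioid are not distinguished.
- **Eligibility** (Inclusion and Exclusion Criteria): long-term opioid use is not an exclusion. The only open-ended criterion is "Other reason at the discretion of clinician/s".
- **Baseline data** (Data To Be Collected): the list includes "Baseline characteristics: age, gender, comorbidities, social history, opioid use". A separate list records opioid intake at baseline, before hospital, in ED before the block, and after the block. No section says how the baseline figure enters the outcome.
- **Choice of block** (Current Practice; Block Standardisation): the treating clinician decides, and the study is observational.
- **Analysis** (Statistical Analysis): the tests listed are t-tests and chi-square tests with no covariates. None is listed for opioid requirement, which is also absent from the bulleted secondary outcomes.
- **Opioid figures** (background audit): "patients receiving PENG blocks required fewer opioids pre operatively (mean = 22.67 mg") against "FIB mean = 26.15 mg and FNB mean = 30.90 mg". The audit included 6 PENG patients, reported p = 0.5, and counted opioid from block to operation.

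**The concern.** The outcome is called a requirement but is measured as total intake. If a patient's regular opioid is continued on the chart after the block, that dose reflects prior treatment and says nothing about how well the block worked. How much of it is counted also depends on when the window opens and when the patient goes to theatre.

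In a randomised trial this would mainly cost precision. Here the clinician picks the block, so nothing in the design makes the proportion of long-term users similar across blocks. An excess in the PENG group would hide a real opioid saving. An excess in the comparator group could create an apparent one. With similar proportions and doses in both groups the expected shift is zero, but the extra variance remains.

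The protocol's case for the PENG block includes reduced opioid exposure in a vulnerable population, and this is its only measure of opioid use after the block.

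**Working it through.** **Inputs from the protocol.** Minimum sample 25 PENG and 49 comparator. The early-termination option is 125 patients with 41 PENG, hence 84 comparator. Audit means from block to operation: PENG 22.67 mg, fascia iliaca 26.15 mg, femoral 30.90 mg. The audit also gives 0 to 6 h means: for PENG "in the 0-6 hours period immediately post block (mean = 3.00 mg"), for fascia iliaca 6.38 mg and for femoral 9.10 mg.

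**Group sizes.** These come from the pain-score calculation (difference 1.5, SD 2.4, one-sided 0.05, power 0.80, ratio 1:2). The normal approximation gives n = (1 + 1/2) × 2.4² × (1.645 + 0.842)² / 1.5² = 23.7, so 24 + 48 = 72. At 25 + 49 the t-test power is 0.809. The stated 74 is therefore reproduced to within two patients. It says nothing about power for opioid intake.

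**Audit differences.**
- Block to operation: 26.15 − 22.67 = 3.48 mg; 30.90 − 22.67 = 8.23 mg.
- 0 to 6 h: 6.38 − 3.00 = 3.38 mg; 9.10 − 3.00 = 6.10 mg.

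**Assumptions.** The protocol gives no prevalence or dose of long-term opioid use. I take regular doses of 30, 60 and 120 mg/day oral morphine equivalent, continued on the chart, with half the daily dose falling in a full 12 h window. Earlier theatre check-in would reduce that amount. An excess user is one beyond the number that would match the other group's proportion at the same dose.

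**Shift in a group mean** = excess users × dose in 12 h / group size. At 60 mg/day with 25 PENG patients this is 30/25 = 1.2 mg per excess user, and 3 × 1.2 = 3.6 mg. The number needed to reach a difference D is D × group size / dose in 12 h, rounded up.

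| Regular dose (mg/day) | In 12 h (mg) | Shift per excess user, 25 PENG (mg) | Needed for 3.48 mg, 25 PENG | Needed for 3.48 mg, 41 PENG | Needed for 3.48 mg, 49 comparator | Needed for 8.23 mg, 25 PENG |
|---|---|---|---|---|---|---|
| 30 | 15 | 0.6 | 6 | 10 | 12 | 14 |
| 60 | 30 | 1.2 | 3 | 5 | 6 | 7 |
| 120 | 60 | 2.4 | 2 | 3 | 3 | 4 |

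**Noise when prevalence is equal.** With an assumed 10% prevalence and 30 mg in 12 h, regular opioid adds an SD of 30 × √(0.1 × 0.9) = 9 mg per patient. At 25/49 this alone contributes a standard error of 9 × √(1/25 + 1/49) = 2.2 mg to the difference.

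A binomial simulation (400,000 draws) gives the probability that chance imbalance alone moves the difference by at least 3.48 mg in either direction, at 10% prevalence:

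| In 12 h (mg) | 25/49 | 41/84 |
|---|---|---|
| 15 | 0.3% | about 0% |
| 30 | 13% | 4% |
| 60 | 46% | 31% |

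At 30 mg in 12 h and 25/49, the probability is 4% at 5% prevalence and 25% at 20%. Any systematic link between prior opioid use and block choice would come on top of this.

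**The case against.** The strongest reply is that this belongs in an SAP. The baseline intake needed for a correction is already collected, and the definition rules out neither subtraction, nor a covariate, nor a subgroup. Adjustment could indeed sit in an SAP not shown here, and its absence is no finding. What remains is the definition itself, which is fixed in the protocol as total charted intake. Separating regular doses also requires flagging them when charts are abstracted, so it is best settled before extraction.

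Three other parts of the opposing case stand:
- The size depends on assumed doses and prevalence. No section says that regular doses are continued after the block, or that clinicians choose blocks according to prior opioid use.
- The 3.48 mg is the smaller of the two block-to-operation contrasts. The main comparison pools femoral and fascia iliaca blocks, so its audit counterpart lies between 3.48 and 8.23 mg, and more excess users would be needed.
- A raw total keeps continuity with the audit, which used total intake. Subtracting regular doses would not remove differences in as-needed use between long-term users and opioid-naive patients.

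A reader might infer that the trial seeks a particular opioid difference that a few long-term users would swamp. The protocol sets none; its only target differences are 1.5 and 1.3 points in pain-score reduction. The audit is merely the available yardstick, and a weak one: 6 PENG patients, not significant, and a window running to operation without the 12 h limit.

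A reader might also infer that the trial's opioid-sparing conclusion rests on this total. Outcomes and Significance argues differently: "If it is a superior regional analgesic then it follows that the therapy should be superiorly opioid-sparing". That sentence reasons from better analgesia and does not refer to this outcome.

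**Conclusion.** The point holds as a correctable weakness in the definition of a secondary outcome. As written, opioid requirement mixes any continuing regular opioid with opioid needed after the block, in a non-randomised comparison that admits long-term users.

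Its practical size is conditional. Under the doses assumed, an imbalance of two to six long-term users in a PENG group of 25 would be as large as the audit's PENG to fascia iliaca difference; at 60 mg/day it takes three. Matching the femoral block difference takes four to fourteen, or seven at 60 mg/day. The larger PENG group of 41, or an imbalance arising in the comparator group, needs more users at most doses.

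The documents do not show that such an imbalance will occur. They support possible bias if users are unevenly spread, and added variance if they are evenly spread. The primary pain outcome and its sample size do not depend on this definition.

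**What to change.** Amend Opioid Requirement in one of two ways, before chart extraction begins:

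1. Define the outcome as oral morphine equivalent given after the block, within the existing window, beyond charted continuing regular doses. Identify those doses from the baseline intake already collected.
2. Keep the total as the outcome, and state that blocks will be compared with adjustment for baseline opioid intake.

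In either case, report the unadjusted raw total as a sensitivity analysis, which also preserves comparability with the audit. A separate comparison in opioid-naive patients is optional; with about 25 PENG patients at the minimum sample it would have low precision.

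The cost is a sentence in the definition and, for the first option, a flag at extraction marking pre-existing regular opioid, hence slightly more abstraction time. No new data source is needed and no patient's care changes. Neither option removes all confounding by prior opioid use.
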